3.3 Definition of dose limiting toxicity

Therapeutic IgGs such as trastuzumab, alemtuzumab or rituximab, and related proteins commonly cause infusion-related reactions. These reactions are thought to be due to cytokine release and typically are most frequent and severe with the first infusion, declining in incidence and severity thereafter. Such reactions are generally managed by slowing or interrupting the infusion. It is possible that MOv18 IgE will cause these non-specific infusion-related reactions, which are biologically distinct from anaphylaxis, although it can be difficult to distinguish them clinically.

Despite pre-clinical evidence suggesting otherwise, it is possible that MOv18 IgE may also cause anaphylaxis due to basophil and/or mast cell degranulation. Such a reaction would be predicted to persist and probably worsen with subsequent infusions. Slowing or interrupting the infusion would typically be insufficient to control such a reaction and systemic therapy, including administration of adrenaline, might be needed.

Clinically, the symptoms, signs and onset of typical cytokine release-type infusion reactions are very similar to those associated with IgE-mediated basophil and/or mast cell degranulation/anaphylaxis and it may be difficult to distinguish these different types of acute reaction in a patient receiving their first dose. However, the presence of urticaria is almost universal in reactions due to mast cell degranulation, but is not typical of infusion reactions seen with protein-based therapeutics such as IgGs (although it can occur). Importantly, emerging data from the CRUKD14001 study indicate that urticaria without systemic symptoms is common with MOv18 IgE and does not necessarily indicate the onset of anaphylaxis. Serum tryptase elevation (a marker of mast cell degranulation) would not be expected to occur with cytokine release-type infusion reactions (Cheifetz *et al.*, 2003), and for this study is considered critical in distinguishing these two types of reactions clinically.

3.3.1 Dose limiting toxicity (DLT)

Dose limiting toxicity is defined as any of the following events occurring in the first 3 weeks of IMP administration that are considered to be probably or highly probably related to MOv18 IgE:

(For dose-independent significant toxicity, see Section 3.3.2)

Non-haematological toxicity

- Any other drug-related non-haematological Grade 3 or 4 toxicity EXCLUDING:
 - Grade 3 or 4 nausea or vomiting, in patients who have not received optimal treatment with anti-emetics
 - Grade 3 or 4 diarrhoea in patients who have not received optimal treatment with anti-diarrhoeals e.g. loperamide and/or codeine
 - Transient Grade 3 biochemical abnormalities that are asymptomatic and considered not to be clinically significant
 - Grade 3 fatigue
- Fatal event

Haematological toxicity

- Grade 4 neutropenia ($ANC < 0.5 \times 10^9/L$) for ≥ 5 days duration *see note
- Febrile neutropenia (fever of unknown origin without clinically or microbiologically documented infection with Grade 3 or 4 neutropenia [$ANC < 1.0 \times 10^9/L$] and fever $\geq 38.5^\circ C$)
- infection (documented clinically or microbiologically) with Grade 3 or 4 neutropenia ($ANC < 1.0 \times 10^9/L$);
- Grade 4 thrombocytopenia (platelets $< 25 \times 10^9/L$)
 - a) for ≥ 5 days *see note, or
 - b) associated with active bleeding, or
 - c) requiring platelet transfusion.

* In the event of a Grade 4 neutropenia or Grade 4 thrombocytopenia, a full blood count must be performed at least five days after the onset of the event to determine if a DLT has occurred. Continue to monitor the patient closely until resolution to Grade 3 or less.

Note that:

- Isolated cutaneous toxicity (urticaria or other skin symptoms/signs) without any associated systemic symptoms or signs and without serum tryptase elevation may not be considered a DLT, if agreed by the Trial Steering Group (TSG) (see Section 3.6 for information regarding the Trial Steering Group). Such patients require premedication (at least for the first subsequent dose) and very close observation if they are given further doses of MOv18 IgE;
- A positive skin prick test is not considered a DLT in this study unless it is associated with systemic symptoms or signs, or an elevated serum tryptase. However, a positive skin prick test is considered an indicator that anaphylaxis might occur if MOv18 IgE were to be given intravenously. Accordingly, positive skin prick tests are an event of interest and must be taken into consideration by the TSG (see Section 3.6) when decisions on dose escalation and/or cohort expansion are made (see also Section 5.5.4).

The dose limiting toxicity (DLT) and maximum tolerated dose (MTD) are defined using the National Cancer Institute (NCI) Common Terminology Criteria for Adverse Events (CTCAE) Version 4.02.

Should any change be made to the grade or causality of an AE during the study that may alter its DLT status, the Centre for Drug Development (CDD) must be informed immediately as this may affect dose escalation decisions.

3.3.2 Dose-independent significant toxicity

Any event judged to be due to systemic IgE-mediated mast cell degranulation (anaphylaxis; see Appendix 5) is considered to be a dose-independent significant toxicity that may have an impact on the future safe use of IgE therapy. Grade 2 or worse anaphylaxis that is probably or highly probably related to MOv18 IgE is considered clinically important and could lead to temporary suspension of recruitment into the trial and/or other restrictions to patient entry (see [Section 3.4.2](#)). Observation of Grade 2 or worse anaphylaxis at a frequency above a pre-determined threshold will lead to permanent cessation of the trial.

3.4 Definition of maximum tolerated dose

3.4.1 Maximum tolerated dose (MTD)

The maximum tolerated dose will be defined as a dose level below the dose level associated with DLT in two out of three patients (or two out of six patients in an expanded cohort). All decisions on dose escalation/de-escalation and cohort expansion/termination will be made by the Trial Steering Group. (see [Section 3.6](#)).

It is possible that the MTD will not be reached in this study.

The RP2D will be determined following discussion of all relevant toxicity and efficacy data by the TSG. All significant toxicities (including those occurring after the first three doses of MOv18 IgE) will be considered in the determination of the RP2D.

3.4.2 Acceptable frequency of dose-independent significant toxicity (anaphylaxis)

Anaphylaxis is an unwanted event driven by effector cell degranulation that is usually triggered by exposure to an allergen. Emerging data from the CRUKD14001 trial indicate that anaphylaxis following exposure to Mov18 IgE can occur, but this is unlikely to be dose-related. Patient-specific factors in an affected patient (such as the presence of pre-existing antibodies to IgE) may be involved. Anaphylaxis is reported following exposure to many other medications, although the frequency of such events is generally low. Therefore, the occurrence of anaphylaxis in a single patient in the CRUK14001 trial does not necessarily indicate that a maximum tolerated dose has been reached, or that recruitment overall, cohort expansion, and/or dose escalation should cease in the CRUKD14001 trial.

Accordingly, for anaphylaxis >Grade 1 within this trial (defined according to Appendix 5), an assessment will be made as to the frequency of these events (taking into account events seen in all patients who received MOv18 IgE). An anaphylaxis frequency of 1% or less is likely to be acceptable, but a frequency of 20% or more unacceptable, based on experience with other medications used in routine oncology practice. Therefore, if any patient experiences >Grade 1 anaphylaxis, recruitment will be suspended and a dose review meeting will take place. Taking into consideration the relatively small numbers of patients that are enrolled in a Phase I trial, the TSG will decide whether further patients should be enrolled, whether the dose escalation and/or cohort expansion may continue and whether there should be further restrictions to patient eligibility (if clear risk factors for anaphylaxis can be identified). The TSG will also take into consideration any equivocal or Grade 1 events, should these occur.

3.5 Patient evaluability

All patients who receive any amount of MOv18 IgE, either by IV infusion or as a skin prick test, will be evaluable for safety. However, dose escalation decisions require at least one or three patients (depending on the cohort) to receive 3 doses of IV MOv18 IgE without DLT (see [Section 5.4](#)).

All eligible patients who receive at least one dose of IV MOv18 IgE and have a baseline and at least one post-baseline disease assessment will be evaluable for response according to RECIST version 1.1 (see Appendix 3). For this study, to be assigned a status of complete response (CR) or partial response (PR), changes in tumour measurements do not need to be confirmed by repeat measurements four weeks later. To be assigned a status of stable disease (SD), follow-up measurements must have met the SD criteria at least once and at least six weeks after the initial dose of MOv18 IgE is given.

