3.2 Design of the Study

This is a multi-centre, first in human, Phase I, open label, dose escalation study. Approximately 25 evaluable patients with advanced, unresectable solid tumours expressing the FR α will be entered into this study. The final number will depend on: the number of dose escalations required to reach DLT, or

to reach a threshold frequency of dose-independent significant toxicity (Section 3.3.2) or to reach the maximum planned dose level (50 mg).

It is expected that the study will take about 4 to 5 years depending upon the number of cohorts explored during dose escalation.

MOv18 IgE will be administered as an IV infusion. Patients in all cohorts will receive a total of six doses of MOv18 IgE at 1-week intervals (over an initial dosing period of 6 weeks). This dosing period, called the 'Initial Treatment Period', is considered a loading phase. During this period, three weeks of treatment is considered one cycle.

Should additional drug supply become available during the study (for example if dose escalation does not proceed through all the planned dose levels), patients in any cohort who appear to be benefitting from MOv18 IgE may be given up to three further doses of MOv18 IgE at fortnightly intervals, starting two weeks after the sixth dose of MOv18 IgE, and continuing at the same dose level as the last dose received. This additional period is considered a maintenance phase. The total number of doses for patients completing the 'Initial Treatment Period' and the 'Maintenance Period' would be 9 over a treatment period of 12 weeks.

Please refer to Figure 3: MOv18 IgE Dosing Schedule in Section 5.3.

It is planned that all patients will receive a flat dose of MOv18 IgE, without adjustment for body weight or surface area. The starting dose will be 70 µg and dose escalation will be carried out through defined dose levels up to a maximum dose of 50 mg (see Section 5.4 Dose Escalation Scheme). However, a switch to weight-based dosing and/or intra-patient escalation will be considered during the course of the trial, if emerging clinical data suggest that this could be beneficial, for example by reducing any large inter-patient variations in PK.

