7.3 Evaluations at First Post-treatment Safety Assessment (28 ±7 days after final dose)

Evaluations at the First Post-treatment Safety Assessment must be performed 28 ±7 days after the final infusion of MOv18 IgE. The following investigations should be done:

- **Symptom-directed physical examination**
- **WHO performance status**
- **Weight**
- **Vital signs**, if clinically indicated
- **ECG**

- **Blood sample for clinical laboratory tests** – Haematology and Biochemistry parameters as detailed in Section 7.1.4
- **Urine sample for urinalysis** – glucose, protein and blood
- **Assessment of AEs and concomitant treatments**
- **Assessment of disease response**: if not performed within previous 28 days per RECIST based on clinical examination, tumour marker, and CT/MRI for patients with measurable disease. Response will be assessed by RECIST 1.1 criteria (see Appendix 3), as well as by CA125 or other tumour marker (Rustin, 2003) if applicable.
- **Tumour marker**, if appropriate for tumour type
- **Research blood samples** as described in Table 6 Summary of PK and PD Assessments (see Section 8.3).

Patients who receive MOv18 IgE as a skin prick test only should be followed for safety until resolution or stabilisation of any AEs/SAEs associated with MOv18 IgE.

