10.2 Timing and type of tumour assessments

A thorough clinical and radiological evaluation of malignancy, as judged appropriate by the Investigator, and in line with the protocol, must be performed before starting the investigational medicinal product (IMP). The same methods that detect evaluable lesions at baseline must be used to follow these lesions throughout the study. To ensure compatibility, the radiological assessments used to assess response must be performed using identical techniques. Imaging based evaluation is preferred to evaluation by clinical examination when both methods have been used to assess the anti-tumour effect of a treatment.

All radiological assessments and clinical measurements to assess response must be performed within 28 days before starting treatment. The interval between the last anti-cancer therapy and these measurements must be at least four weeks (28 days).

For this study, due to the limited duration of study treatment, complete (CR) and partial responses (PR) do not need to be confirmed by a subsequent assessment at least 4 weeks later. Stable disease criteria must be met at least once after study entry at a minimum interval of six weeks to be defined as stable disease (SD). Possible contribution of inflammatory cell infiltration to transient enlargement of tumours may be considered when assessing response and considering discontinuation of study treatment. Evaluation by tumour marker such as CA125 may be used for patients without measurable disease.

Copies of the scans must be available for external independent review if requested by the CDD.

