10.2.1 Baseline evaluations

These must include radiological measurements of lesions in the chest and abdomen by CT scan or MRI scan and/or other radiological measurements as clinically indicated or clinical measurements as appropriate e.g. assessment of palpable lesions or measurement of tumour markers. All areas of disease present must be documented (even if specific lesions are not going to be followed for response) and the measurements of all measurable lesions must be recorded clearly on the scan reports. Any non-measurable lesions must be stated as being present. For clinical measurements, documentation by colour photography including a ruler to estimate the size of the lesion is strongly recommended, as this aids external independent review of responses. (See Appendix 3 Section 1.2.1 of RECIST criteria)

10.2.2 Evaluations during the study and at 'First Post-treatment Safety Assessment' 28 ±7 days after final dose)

Tumour assessments must be repeated every six weeks (i.e. after the first 6 doses during the Initial Dosing Period and again after 3 doses in the Maintenance Period) or more frequently, if clinically indicated. All lesions measured at baseline must be measured at every subsequent disease assessment and recorded clearly on the scan reports. All non-measurable lesions noted at baseline must be noted on the scan report as present or absent.

All patients, who are removed from the study for reasons other than progressive disease, must be re-evaluated at the time of treatment discontinuation, unless a tumour assessment was performed within the previous four weeks.

It is the responsibility of the Principal Investigator to ensure that the radiologists are aware of the requirement to follow-up and measure every target lesion mentioned at baseline and comment on the non-target lesions in accordance with RECIST criteria.

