10.3 Tumour response

All patients who meet the eligibility criteria, receive at least one dose of study drug and have a baseline and at least one post-baseline assessment of disease will be evaluable for response. Patients who develop clear evidence of progressive disease (PD) without a formal disease assessment will be considered non-responders. There is no requirement for repeat assessments to be performed in order for a patient to be assigned a status of CR or PR in this study. To be assigned a status of stable disease (SD), tumour response measurements must have met the SD criteria at least once and at least six weeks after the first dose of the investigational medicinal product (IMP) MOv18 IgE is given.

Tumour response should be classified as “not evaluable” (NE), only when it is not possible to classify it under another response category, for example, when baseline and/or follow-up assessment is not performed or not performed appropriately.

Expert reviewers appointed by CDD may undertake an independent review of all the Investigator's assessed objective responses (CR and PR). The expert reviewers will include at least one specialist who is not an Investigator in the study. The independent reviewer's assessment will also be documented in the final clinical study report (CSR) along with the assessment made by the Investigator. The eCRF will reflect the Investigator's opinion.

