2.4.3. Best overall response: all time points

The best overall response is determined once all the data for the patient is known.

Best response in these trials (in which confirmation of complete or partial response is NOT required): is defined as the best response across all time points (for example, a patient who has SD at first assessment, PR at second assessment, and PD on last assessment has a best overall response of PR). When SD is believed to be best response, it must also meet the protocol specified minimum time from baseline. If the minimum time is not met when SD is otherwise the best time point response, the patient's best response depends on the subsequent assessments. For example, a patient who has SD at first assessment, PD at second and does not meet minimum duration for SD, will have a best response of PD. The same patient lost to follow-up after the first SD assessment would be considered inevaluable. A 'positive' FDG-PET scan lesion means one which is FDG avid with an uptake greater than twice that of the surrounding tissue on the attenuation corrected image.

Table 1 – Time point response: patients with target (+/-non-target) disease

Target lesions	Non-target lesions	New lesions	Overall response
CR	CR	No	CR
CR	Non-CR/non-PD	No	PR
CR	Not evaluated	No	PR
PR	Non-PD or not all evaluated	No	PR
SD	Non-PD or not all evaluated	No	SD
Not all evaluated	Non-PD	No	NE
PD	Any	Yes or No	PD
Any	PD	Yes or No	PD
Any	Any	Yes	PD

CR = complete response, PR = partial response, SD = stable disease, PD = progressive disease, and NE = inevaluable.

Table 2 – Time point response: patients with non-target disease only

Non-target lesions	New lesions	Overall response
CR	No	CR
Non-CR/non-PD	No	Non-CR/non-PD(a) NE
Not all evaluated	No	PD
Unequivocal PD	Yes or No	PD
Any	Yes	

CR = complete response, PD = progressive disease, and NE = inevaluable.

(a) 'Non-CR/non-PD' is preferred over 'stable disease' for non-target disease since SD is increasingly used as endpoint for assessment of efficacy in some trials so to assign this category when no lesions can be measured is not advised.

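### Stable disease needs an assessment on Day 43 or later, but the text permits the on-treatment scan on Days 37-42 and can then waive the next one; the six-week clock also has conflicting starting points

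*Protocol*

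**What the plan says.** **The SD rule.** Protocol Section 3.5 requires the SD criteria to be met "at least once and at least six weeks after the initial dose of MOv18 IgE is given". Section 10.3 uses the same clock: "tumour response measurements must have met the SD criteria at least once and at least six weeks after the first dose".

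**Other starting points.** Section 10.2 reads: "Stable disease criteria must be met at least once after study entry at a minimum interval of six weeks". Appendix 3, Section 2.4.3, says of SD as best response that "it must also meet the protocol specified minimum time from baseline".

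**When the scan is due.** Section 10.2.2 asks for assessments every six weeks and explains this as "after the first 6 doses during the Initial Dosing Period". Section 7.2.4 asks for one every two cycles, under a heading that places it in the 24 hours before a new cycle's Day 1 infusion. Table 4 says only that it is six-weekly. None of these gives a study day or a window.

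**When the next scan is waived.** Section 7.3 requires a disease assessment 28 ±7 days after the last dose, but only "if not performed within previous 28 days per RECIST".

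**Who is evaluable.** Sections 3.5 and 10.3 count any eligible patient with at least one dose, a baseline assessment and at least one post-baseline assessment as evaluable for response.

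**The concern.** Section 10.2.2 treats two different times as the same: six weeks from the start, and the point after six weekly doses, which is reached at five weeks. The SD rule follows the first, while a site may reasonably follow the second. A site that scans soon after dose 6 obtains an assessment too early for SD, and the 28-day waiver can remove the scan that would have repaired this.

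The conflict over the clock is separate. Baseline imaging can precede dosing by up to four weeks, so two analysts could classify the same scan differently, each citing the protocol.

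Best response is a secondary endpoint, and Section 3.1 lets evidence of anti-tumour activity contribute to the recommended Phase II dose. With about 25 evaluable patients, an SD category lost only through scan timing is an avoidable loss.

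**Working it through.** **Inputs.** Dosing is "six doses of MOv18 IgE at 1-week intervals (over an initial dosing period of 6 weeks" (Section 3.2). The SD minimum is 42 days after first dose (Sections 3.5 and 10.3). The first post-treatment visit is 28 ±7 days after the last dose, and its scan is waived if one was done in the previous 28 days (Section 7.3). Baseline: "All radiological assessments and clinical measurements to assess response must be performed within 28 days before starting treatment" (Section 10.2). First dose is Day 1, with no dose delays.

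**1. The plan's own six weeks.** Dose k falls on Day 1 + 7(k − 1), so dose 6 is on Day 1 + 35 = Day 36, five weeks after first dose. Six weeks is Day 1 + 42 = Day 43. The figure reproduces as two full 21-day cycles (2 × 21 = 42 days), but not as the point after dose 6.

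**2. The slot in the Section 7.2.4 heading.** The next cycle's Day 1 would nominally be Day 43. The preceding 24 hours can fall on Day 42, one day short.

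**3. The waiver.** The post-treatment visit is nominally Day 36 + 28 = Day 64, with a range of Days 57-71 (15 days). A scan on day s is s − 1 days after first dose. The later scan is waived if visit day − s ≤ 28.

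| Scan day | Days after first dose | Long enough for SD? | Scan's age at Day 64 | Visit days (of 15) with scan waived |
|---|---|---|---|---|
| 37 | 36 | no | 27 | 9 (to Day 65) |
| 38 | 37 | no | 26 | 10 (to Day 66) |
| 39 | 38 | no | 25 | 11 (to Day 67) |
| 40 | 39 | no | 24 | 12 (to Day 68) |
| 41 | 40 | no | 23 | 13 (to Day 69) |
| 42 | 41 | no | 22 | 14 (to Day 70) |
| 43 | 42 | yes | 21 | 15 (to Day 71) |

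At the nominal visit, all six early scan days trigger the waiver. Over the whole window, 9 + 10 + 11 + 12 + 13 + 14 = 69 of 6 × 15 = 90 scan-visit combinations do so, and 21 still require a scan. This counts calendar combinations and is not a probability.

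**4. The category that results.** Appendix 3, Section 2.4.3, makes best response depend on subsequent assessments when SD comes too early. If the next scan is waived, there may be none. The patient is in the evaluable set of Sections 3.5 and 10.3 without an assignable SD.

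**5. The clocks.** With baseline b days before first dose, the interval from baseline is (s − 1) + b. It reaches 42 days when b ≥ 43 − s, that is, b ≥ 6 for a Day 37 scan and b ≥ 1 for a Day 42 scan. Up to 28 days is allowed. Example: a Day 40 scan with a Day −20 baseline is 39 days from first dose (not SD) but about 60 days from baseline (SD). Section 10.2 does not say which date study entry is.

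**The case against.** The strongest reply is that the scan is meant to be six-weekly. Section 10.2.2 says so before its parenthesis, Table 4 repeats it, and Section 7.2.4 ties it to two three-week cycles. Read together, these point to about Day 42-43, which leaves a one-day near miss instead of a six-day band. That is a fair reading, but the text does not require it: Section 10.2.2 supplies its own explanation, and no window overrides it.

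The waiver is also not absolute. It lapses when the visit comes more than 28 days after the scan. Maintenance patients have a later scan, dose delays push the scan later, and extra scans are allowed if clinically indicated. All of this stands and limits the reach of the problem.

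On the clock, the two operative definitions (Sections 3.5 and 10.3) agree on first dose. Appendix 3 is an abridged guideline that defers to the protocol's minimum time, and its Section 2.6.3 measures SD duration from the start of treatment. This shows which clock was probably intended, but it does not remove the conflicting words in Section 10.2 and Appendix 3, Section 2.4.3.

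A reader might infer that truly stable patients become inevaluable as a rule. The documents do not support that. The inevaluable example in Appendix 3 is a patient lost to follow-up, not one who attends and has a scan waived, and Section 10.3 reserves not-evaluable status for cases that fit no other category. Nor can the band of early days be turned into a percentage of patients, because the protocol gives no distribution of scan days.

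**Conclusion.** The concern holds as a conflict between stated rules. On one permitted reading, an on-treatment scan on Days 37-42 cannot support SD, and the nominal post-treatment scan is then waived. Separately, the six-week minimum has conflicting starting points that can change the category of the same scan.

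The number of patients affected is unknown. It is none if all sites scan on Day 43 or later. At most it is every stable six-dose patient who was scanned on Days 37-42, whose post-treatment visit came within 28 days of that scan, and who had no other later scan. The day counts assume weekly dosing without delay.

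The impact is modest. Only SD is affected; complete response, partial response and progression carry no minimum interval here. Section 13.5 plans to present best overall response in listings only. The change is still worth making because it is cheap and the loss is avoidable.

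**What to change.** 1. Use six weeks from first dose as the only clock, in Sections 3.5, 10.2 and 10.3 and in Appendix 3, Section 2.4.3.
2. State the on-treatment assessment window as Day 43-49 in Sections 7.2.4 and 10.2.2 and in Table 4. This ends before a first maintenance dose at its nominal Day 50 (Day 36 + 14).
3. Apply the 28-day waiver in Section 7.3 only when the earlier scan was on or after Day 43, or already showed complete response, partial response or progression.

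With the second change, every on-schedule scan meets the interval. With the third, a patient scanned too early is rescanned on Days 57-71, which is 56-70 days after first dose, and can be classified.

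The cost is wording, plus an occasional scan that Section 7.3 already schedules and would no longer waive. No dose or treatment rule changes.
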